8.2 Accrual

It is estimated that up to 8-12 research participants will be enrolled each month and that approximately 12-15 months of accrual will be necessary to enroll 90 evaluable participants.

8.3 Study Duration

Each subject's participation in the study will be 24 months, with clinic visits occurring during the first 12 months and a remote safety assessment at 24 months. Given that accrual will take up to 15 months it is estimated that the remote safety assessment will be conducted on that last patient 39 months (3.25 years) after the study opens.

8.4 Primary and Secondary Endpoints

The primary endpoint of this study is the difference between a child's observed and expected changes in GMFM-66 score 12 months after the initial study infusion. This study will provide separate interval estimates of the mean of this outcome measure in patients assigned to the hC-MSC, AlloCB, and Natural History arms at 12-months. The secondary endpoint of this study is the number of adverse events occurring over a 12-month period post-treatment with hCT-MSC or AlloCB.

8.5 Sample Size and Power Calculations

The sample size for this study was selected to provide a high level of precision for estimating the mean of the observed minus expected 12-month change on the GMFM-66 in each of the study arms, and to provide a high probability of detecting commonly occurring adverse events after infusion with AlloCB or hCT-MSC.

As shown in the table below, a sample size of 30 patients per group provides a 95.8% probability of detecting common adverse events that occur in 10% of infusions (with hCT-MSC or AlloCB). This sample size also provides a 78.5% probability of observing events that occur in 5% of infusions, and a 26.0% probability of observing rare events that occur in 1% of infusions.

	Probability (%)*				
	N=20 N=30 N=40 N=50				
True Probability of an Event (%)	/ of an Event (%)				
1	18.2	26.0	33.1	39.5	
5	64.2	78.5	87.1	92.3	
10	87.8	95.8	98.5	99.5	
20	98.8	99.9	100.0	100.0	
50	100.0	100.0	100.0	100.0	

Probability of Observing One or More Events with Various Sample Sizes*

*Binomial probability of 1 or more independent events.

The sample size for this study must also support estimation of the mean observedminus-expected GMFM-66 change score at 12 months post-intervention with MSC, AUCB, and in the Natural History arm. Thus, three interval estimates will be constructed using the t-distribution as follows.

$$\left(\bar{x}-t\alpha_{/2}*\frac{s}{\sqrt{n}},\bar{x}+t\alpha_{/2}*\frac{s}{\sqrt{n}}\right)$$

The margin of error *E* is the confidence interval half-width:

$$E = t\alpha_{/2} * \frac{s}{\sqrt{n}}$$

The margin of error for this study was selected as 2 points with a confidence level of 95%. The following formula was solved iteratively to obtain the sample size for each treatment group.

$$N = \left(\frac{t\alpha_{/2} * s}{E}\right)^2$$

The standard deviation, *s*, was estimated using 36 participants in the CP-AC trial who met age and GMFCS inclusion criteria for the present study: 5.16 (95% CI: 4.18, 6.13).

Starting with a sample size of 20, and assuming a standard deviation of 5.16, a total of 3 iterations were required to reach a final group sample size of 28 as shown in the table below.

Iteration #	Starting N	Degrees of Freedom	$t\alpha_{/2}$	Ending N
1	20	19	2.093	29
2	29	28	2.048	28
3	28	27	2.052	28

8.6 Analysis Plan

8.6.1 Analysis Populations

The following populations are defined to support analyses of the primary and secondary endpoints.

Intention to Treat Population

This population will include all enrolled and randomized participants according to their assigned treatment. The primary endpoint will be evaluated in this population.

Safety Population

The safety population defines the patients in whom the secondary endpoint will be evaluated and will include all subjects who received at least 1 infusion. Analyses of the Safety Population will be conducted using an as-treated approach, which considers each patient according the treatment actually received rather than the treatment they were assigned.

8.6.2 Timing of Analyses

The analysis of the primary and secondary outcome measures will be conducted when the last patient reaches their 12-month visit. An update will be made to the safety analyses when the last patient reaches their 24-month visit.

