4.3 Study Endpoints

Primary Endpoint:

The primary endpoint is the difference between a participant's observed and expected changes in GMFM-66 score 12 months after the initial study infusion. Interval estimates will be reported separately for the hCT-MSC, AlloCB, and Natural History arms. Expected GMFM-66 scores at 12 months will be calculated based on the participant's baseline age, GMFCS level, and GMFM-66 score at study entry using published reference percentiles.⁶⁴

Secondary Endpoints:

The secondary endpoint is the number of adverse events occurring over the 12-month period post-infusion with hCT-MSC or AlloCB.

Exploratory Analyses:

- Observed GMFM-66 score at baseline, 6, and 12 months
- Change in the Peabody Developmental Motor Scale-2 (PDMS-2) score at 6 and 12 months.
- Change in normalized total brain connectivity, as measured by brain MRI with DTI, from baseline to 12 months.
- Change in functional and quality of life measures at 6 and 12 months.

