8.0 STATISTICAL CONSIDERATIONS

8.1 Study Design

This study is a phase I/II, prospective, randomized, open-label trial designed to provide interval estimates of the 12-month change in motor function after treatment with AlloCB and hCT-MSC, provide additional data to the clinical trials community on the natural history of the motor function in CP over short-term (less than 1 year) time periods relevant to conduct of clinical trials, and assess the safety of repeated doses of hCT-MSC and a single dose of AlloCB in children with cerebral palsy.

Children ages 2-5 years with cerebral palsy due to hypoxic ischemic encephalopathy, stroke, or periventricular leukomalacia will be eligible to participate. All participants will ultimately be treated with an allogeneic cell product at some point during the study. Participants will be randomized (1:1:1) to one of three arms: (1) the "AlloCB" arm will receive one allogeneic CB infusion at the baseline visit; (2) the "MSC" arm will receive three hCT-MSC infusions, one each at baseline, three months, and six months; the "natural history" arm will not receive an infusion at baseline but will receive an allogeneic CB infusion at 12 months. The occurrence of adverse events will be evaluated at 3, 6, 12, and 24 months post-randomization in all participants. Motor function outcome measures will be assessed at baseline, six-months, and one-year time points in all participants. Duration of study participation will be 24 months from the time of the baseline visit. Randomization will be stratified by GMFCS Level (I/II or III/IV) and etiology of CP (Stroke vs. Other).

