8.6.4 Analysis of the Primary and Secondary Endpoints

The occurrence of adverse events in the Safety Population will be summarized descriptively in tables and figures for all subjects and separately by treatment received. Estimates of the mean observed-minus-expected GMFM-66 change score at 12 months will be reported in the Intention to Treat Population along with 95% confidence intervals as described above.

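### The 12-month post-infusion adverse-event endpoint is analysed while most Natural History children, infused only at month 12, are still inside their window

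*Combined protocol and SAP*

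**What the plan says.** Section 4.3 defines the endpoint: "The secondary endpoint is the number of adverse events occurring over the 12-month period post-infusion with hCT-MSC or AlloCB". Section 8.4 repeats it as "the number of adverse events occurring over a 12-month period post-treatment with hCT-MSC or AlloCB". Under 8.1 the Natural History arm "will not receive an infusion at baseline but will receive an allogeneic CB infusion at 12 months".

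Section 8.6.2 sets two cuts. The first: "The analysis of the primary and secondary outcome measures will be conducted when the last patient reaches their 12-month visit". The sentence after it adds: "An update will be made to the safety analyses when the last patient reaches their 24-month visit".

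Section 8.6.1 puts every child with at least one infusion in the Safety Population and applies an as-treated rule that "considers each patient according the treatment actually received rather than the treatment they were assigned". Section 8.6.4 has adverse events "summarized descriptively in tables and figures for all subjects and separately by treatment received".

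No section says how a child whose window is still open at the first cut is counted, whether counts are set against follow-up time, or which of the three hCT-MSC infusions starts the 12 months.

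**The concern.** The endpoint's window and the date of its analysis do not fit for one arm of three. A Natural History child enters the Safety Population at month 12 and completes the 12-month window at month 24, yet the analysis named for this endpoint is triggered when the last child reaches month 12. These children count in the all-subjects display however AlloCB is grouped.

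Counts per child after month-12 AlloCB will therefore be low at that cut because of the calendar alone. Early infusion reactions are little affected; later events are. Assessing safety is a stated purpose of the study (1.0, 8.1), so a reader should not take the first table for a full 12-month count.

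**Working it through.** **Inputs.** 30 per arm, 90 in total (8.5); 1:1:1 allocation and AlloCB at month 12 for Natural History (8.1); accrual A from 8.2, "approximately 12-15 months of accrual will be necessary to enroll 90 evaluable participants"; 24 months of participation per child (8.1, 8.3). **Assumptions not in the plan:** uniform enrolment over A, no dropout, infusions and visits on schedule.

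1. *The plan's own timeline.* 8.3 puts the last remote assessment at study month 39: 15 + 24 = 39, which reproduces. With A = 12 it is 36.
2. *The cuts.* First cut at A + 12, study month 24-27. Update at A + 24, study month 36-39.
3. *Follow-up at the first cut.* A Natural History child enrolled at month e is infused at e + 12. Follow-up is (A + 12) − (e + 12) = A − e, capped at 12. The share of windows still open is min(1, 12/A).
   - A = 12: 30 of 30 open; mean 6.0 months; 30 × 6.0 = 180 of 360 child-months.
   - A = 15: 30 × 12/15 = 24 of 30 open; mean 0.8 × 6 + 0.2 × 12 = 7.2 months; 30 × 7.2 = 216 of 360 child-months.
4. *Pooled AlloCB.* (360 + 180)/720 = 75% and (360 + 216)/720 = 80% of planned child-months.
5. *All subjects, hCT-MSC window from the first infusion.* (360 + 360 + 180)/1080 = 83% and (360 + 360 + 216)/1080 = 87%.
6. *All subjects, hCT-MSC window from the third infusion (month 6).* hCT-MSC follow-up is A − e + 6, capped at 12, with share open 6/A. That leaves 15 of 30 (A = 12) or 12 of 30 (A = 15) hCT-MSC windows open, with means 0.5 × 9 + 0.5 × 12 = 10.5 and 0.4 × 9 + 0.6 × 12 = 10.8. Coverage becomes (12 + 6.0 + 10.5)/36 = 79% and (12 + 7.2 + 10.8)/36 = 83%.
7. *Sensitivity to accrual.* If 12 per month enrol in the first 3 of 15 months (36 of 90, or 40%), 18 of 30 windows are open. With the rest spread evenly over the other 12 months, the mean is 0.4 × 12 + 0.6 × 6 = 8.4 months and pooled AlloCB holds (360 + 252)/720 = 85%. In the other direction, the 8-12 per month in 8.2, if sustained, fills the trial in 90/12 = 7.5 to 90/8 = 11.25 months, and all 30 windows are open.
8. *The 24-month update.* Follow-up is (A + 24) − (e + 12) = A − e + 12, never below 12. The last child has exactly 12 months, with no slack, while 7.9 allows assessments within a month of the time point and 7.4 postpones an infusion for illness.

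Coverage is an upper bound on what is captured. After month-12 AlloCB, the scheduled contacts are the day-after visit, the two-week contact and the remote 24-month assessment (6.6, 7.9). Children given AlloCB at baseline are also seen at 6 and 12 months.

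**The case against.** The strongest reply is that 8.6.2 already deals with this. Its next sentence updates the safety analyses at month 24, and 8.6.1 ties the Safety Population to the secondary endpoint, so the update naturally covers it. The first table is descriptive. Safety oversight during the trial rests on the stopping guidelines (9.5) and the DSMB (10.0), not on this table. Baseline AlloCB, and hCT-MSC if its window runs from the first infusion, are complete at the first cut. All of that stands, and it confines the problem to the first cut. It does not remove it, because 8.6.2 assigns the analysis of the secondary endpoint to that cut and calls the later one only an update.

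Four stronger readings might be inferred, and the documents do not support them.

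- *The plan is silent on pooling.* It is not: the as-treated rule and display by treatment received imply one AlloCB group. What is missing is an explicit statement and a split by infusion time.
- *Baseline AlloCB will look up to twice as harmful as month-12 AlloCB.* Coverage of 50-60% would give a ratio of 1.67-2.0 (1/0.60 to 1/0.50), but only in a split display that the plan does not call for, and only with equal constant event rates and full capture.
- *hCT-MSC will be judged worse than AlloCB.* The plan makes no formal comparison of adverse events between treatments.
- *Everything evens out at month 24.* The windows essentially close if visits are on time, but contacts after month 12 remain sparser.

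**Conclusion.** The concern holds for the first safety table. At the cut that 8.6.2 names for the secondary endpoint, 24-30 of 30 Natural History windows are open under uniform 12-15 month accrual, with a mean of 6.0-7.2 of 12 months observed. The count is about 18 if 15-month accrual is front-loaded and 30 if the stated monthly rate is sustained. Under uniform accrual, pooled AlloCB has at most about 75-80% of its planned child-months, and the all-subjects display about 83-87% with the hCT-MSC window from the first infusion. Fewer events still may be captured, because later contacts are sparse.

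Alpha, power and the primary endpoint are unaffected. This should be corrected, but it is a matter of labelling and display, not a flaw in the design.

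**What to change.** - **8.6.2:** make the 24-month cut the definitive analysis of the secondary endpoint, and label the 12-month safety summary as interim for month-12 infusions.
- **8.6.4:** show baseline AlloCB and month-12 AlloCB separately as well as pooled. For each, give the number with a complete 12-month window, the child-months of post-infusion follow-up and the events per child-month. Note that interim rates after month-12 infusion may still be low because contacts are sparser; dividing by time does not correct that.
- **4.3 and 8.4:** state which hCT-MSC infusion starts the 12-month window.
- **Separate wording points to reconcile:** 7.1 counts the remote 24-month assessment from infusion, while 6.6, 8.1 and 8.3 run from baseline or study entry; for Natural History children these differ by 12 months. Section 8.1 evaluates adverse events at 3 months in all participants, while 7.1 and 7.9 schedule month 3 for the MSC arm only.

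The cost is SAP wording and extra table columns from data already collected. The definitive safety result moves from study month 24-27 to study month 36-39, a cut already planned.

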8.6.3 Demographics, Baseline Characteristics, and Disposition

Demographics and baseline characteristics will be summarized for all research participants and separately by randomized assignment. Characteristics to be examined include age, sex, race/ethnicity, baseline GMFM-66 score, GMFCS level, and etiology of CP. The number of participants entering and completing the study will be diagrammed using the CONSORT guidelines.

8.6.4 Analysis of the Primary and Secondary Endpoints

The occurrence of adverse events in the Safety Population will be summarized descriptively in tables and figures for all subjects and separately by treatment received. Estimates of the mean observed-minus-expected GMFM-66 change score at 12 months will be reported in the Intention to Treat Population along with 95% confidence intervals as described above.

9.0 SAFETY AND ADVERSE EVENT REPORTING

9.1 Definitions

Adverse Event (AE): An adverse event is any untoward medical occurrence associated with the use of the investigational product regardless of whether it is considered related to the investigational product.

Serious Adverse Event (SAE): An adverse event or suspected adverse reaction is considered "serious" if, in the view of either the investigator or sponsor, it results in any of the following outcomes: death, a life threatening adverse event, inpatient hospitalization or prolongation of existing hospitalization, a persistent or significant incapacity or substantial disruption of the ability to conduct normal life functions, or a congenital anomaly/birth defect. Important medical events that may not result in death, be life-threatening, or require hospitalization may be considered serious when, based upon appropriate medical judgment, they may jeopardize the patient or subject and may require medical or surgical intervention to prevent one of the outcomes listed in this definition.

Grade/Severity: Grade/severity will be assessed according to CTCAE v4.0 guidelines.

Suspected Adverse Reaction: A suspected adverse reaction is any adverse event for which there is a reasonable possibility that the investigational product caused the adverse event. "Reasonable possibility" means there is evidence to suggest a causal relationship between the investigational product and the adverse event.

Causality: The investigator will use the following question when assessing causality of an adverse event to the investigational product: "Is there a reasonable possibility that the investigational product caused the event?" An affirmative answer designates the event as a suspected adverse reaction.

9.2 Adverse Event Reporting

All adverse events reported or observed during the study beginning at the time of enrollment must be recorded. Information to be reported includes when the site became aware of the event, investigator-specified assessment of severity and relationship to study therapy, whether there is an alternative etiology, seriousness, as well as any required treatment or evaluations, and outcome. In general, investigators should report adverse events as diseases or syndromes whenever possible, instead of reporting individual component symptoms, signs, laboratory abnormalities, and sequelae.

Severe adverse infusion reactions (fatal, life-threatening or requiring hospitalization) will be reported within seven calendar days of receipt of the information. All fatal or life threatening SAEs will be reported by the investigator or its representatives to the FDA by telephone or fax within seven calendar days after receipt of the information, following FDA guidelines. All serious and unexpected AEs will be reported to the FDA via a written report within 15 days of receipt of the information (21 CFR 312.32). If the principal investigator assesses an event to be unrelated to the study, then the event will not require expedited reporting but will be included in the annual summary report.

The following events within 24 hours of study product infusion will be also be recorded in the e-CRF: allergic reaction/hypersensitivity, sinus bradycardia, sinus tachycardia,

hypertension, hypotension, fever in the absence of neutropenia, rigors/chills, nausea, vomiting, infection with unknown ANC, dyspnea, hypoxia, and hemoglobinuria.

9.3 Serious Adverse Event Reporting

The Principal Investigator or its representative will be responsible for telephone or fax reporting of any unexpected SAEs to the FDA. The Principal Investigator or its representative will notify the FDA by telephone or fax of any fatal or life threatening experience (expedited report) associated with the use of the study therapy as soon as possible but no later than seven calendar days after receipt of the information. Initial notification will be followed by a written report within 15 calendar days. For SAEs associated with the use of the study therapy, the Principal Investigator will notify the FDA as soon as possible, but no later than 15 days, of the initial receipt of the information. The Principal Investigator or Sub-Investigator is responsible for informing the Institutional Review Board (IRB) and DSMB of any study related and unexpected SAEs.

9.4 Eliciting Adverse Event Information

In addition to research participant observations, AEs will be documented from any data collected throughout the study including clinically significant laboratory values or physical exam findings.

9.5 Stopping Guidelines

The following stopping guidelines will be monitored during the duration of the study. The stopping guidelines will be monitored by the CRO, The EMMES Corporation, and are to be used to indicate boundaries requiring discussion by the investigators and DSMB. The study will be stopped for a safety review if:

- Any subject experiences a grade 4-5 infusion reactions within 24 hours of infusion; OR
- Two or more grade 4-5 adverse events determined to be temporally related by the medical safety monitor and/or the DSMB occur; OR
- Any subject experiences a blood stream infection within 6 months of infusion; OR
- Any death.

9.6 Subject Replacement

The sponsor may replace any subject who has not been dosed.

10.0 DATA SAFETY MONITORING BOARD (DSMB)

A DSMB will be formed and a charter established. Members of the DSMB will be independent of Duke University. The DSMB will be notified immediately for all SAEs directly related to the study product throughout the study. A total safety assessment will be prepared on an annual basis and forwarded to the DSMB for review as well. Policies of the DSMB will be described in the DSMB charter and signed by all members.

11.0 DATA HANDLING AND QUALITY ASSURANCE

11.1 Case Report Forms

As part of the responsibilities assumed by participating in the study, the Principal Investigator or Sub-Investigators agree to maintain adequate case histories of the research participants treated as part of the research under this protocol. The Principal Investigator or Sub-Investigator agrees to maintain accurate CRFs and source documentation as part of the case histories.

EMMES will supply the CRF electronically (eCRF) through an electronic data entry system. All eCRFs should be completed by the clinical site. An authorized user at the clinical center completes the initial screening by entering in the research participant demographics and inclusion/exclusion criteria on the eligibility form. Upon enrollment, a form submission schedule is generated for each participant, and displayed as a grid of forms by study visit, that permits direct access to each eCRF for data entry. All CRF information is to be filled in. If an item is not available or is not applicable, an exception can be requested through the data system. Corrections to data fields can be made in the eCRF which maintains a data audit trail.

11.2 Video Recordings

Video recordings of potential subjects from parents and guardians may be submitted and used for determining study eligibility. Video recordings may also be obtained of portions of the motor evaluations if indicated with parental consent, and may include full facial features. The recordings will be used solely for analysis by the research team. They will be stored electronically on a password-protected server.

11.3 Inspection of Records

The Principal Investigator or Sub-Investigators and institutions involved in the study will permit study-related monitoring, audits, IRB review, and regulatory inspection(s) by providing direct access to all study records. In the event of an audit, the Principal Investigator or Sub-Investigator agrees to allow the Food and Drug Administration (FDA), or other regulatory agency access to all study records. The Principal Investigator or Sub-Investigators should promptly notify all relevant parties of any audits scheduled by any regulatory authorities and promptly forward copies of any audit reports received to the both.

